Animal and human studies have demonstrated that moderate intensity exercise when compared to exertional exercise or strength training result in shifting of cytokine expression toward anti-inflammation and diminished markers of oxidative stress.^{7,16,24,35,45} The benefit of early exercise in AIS and sICH in decreasing pro-inflammatory factors has been demonstrated in animal models when exercise is introduced between 24 hours and three days in AIS and at three or four days in sICH.^{40,53-55} An exercise intervention that is standardized in frequency with measureable intensity and duration is necessary to explore the effects of an exercise intervention in acutely ill patients with AIS and sICH. We hypothesize that a balancing of the inflammatory response after sICH can occur with the application of moderate exercise in the acute period.

Objectives (include all primary and secondary objectives)

Primary Objective: to determine the effects of twice-daily, lower extremity CE of 20 minutes duration plus usual care, compared to usual care alone, on the trajectories of M1 versus M2 cytokine phenotypes in the serum and cerebrospinal fluid (CSF).

Secondary Objectives:

- (i) To determine the effects of twice-daily, lower extremity CE of 20 minutes duration plus usual care compared to usual care alone and a third retrospective cohort of patients receiving usual care during the COVID-19 pandemic on, the immediate and sustained physical impairment, disability scores and relevant covariates such as delirium and hospital acquired infections at NCCU discharge and 30 days after hemorrhage.
- (ii) To determine the correlation between serum and cerebrospinal fluid cytokines in patients with external CSF drainage as part of their care.
- (iii) To explore the relationship between pre-morbid physical function and quality of life and changes in inflammatory factors among all participants.
- (iv) To determine the effects of twice-daily, lower extremity CE of 20 minutes duration plus usual care alone on hemispatial neglect as measured by the Sunnybrook Neglect Assessment Procedure on day 1 of the study at transfer from the ICU or discharge from the hospital and 30 days after hemorrhage.

2. Background (briefly describe pre-clinical and clinical data, current experience with procedures, drug or device, and any other relevant information to justify the research)

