- a) A 2 teaspoon sample of the patient's serum on the day of enrollment and two additional times during the seven day study period timed with routine collection of blood, when possible, for daily blood tests while the patient is in the hospital. Blood samples will be collected from an existing arterial or central line or via venipuncture. The initial blood sample will be collected on study day 1 prior to cycling in the intervention group and between 8 am-12 pm in the control group. Subsequent samples will be drawn after the second cycling session and between 2 pm and 6 pm in the control group.
- b) A 4-5 mL sample of saliva on the day of enrollment and two additional times during the seven day study period. Saliva will be collected between 8 am-10 am in all participants and prior to the first cycling session of the day for the intervention group.
- c) A 4 mL sample of cerebrospinal fluid (CSF) on the day of enrollment and two additional times during the seven day study period timed with collection of other sampling, when an external ventricular drain is in place as a part of care. CSF sampling will occur in patients with an external ventricular drain inserted as part of their care and will end after 3 samples or when the drain is discontinued. Efforts will be made to time CSF sampling with planned sampling, if possible and sampling will be performed by a nurse or physician study team member trained in the skill as part of their job using aseptic technique. The initial CSF sample will be collected on study day 1 prior to cycling in the intervention group and between 8 am-12 pm in the control group. Subsequent samples will be drawn after the second cycling session and between 2 pm and 6 pm in the control group.

All samples will be placed on dry ice, centrifuged and stored in a -70 degree Celsius freezer within 1 hour of obtaining the sample. Samples will be labeled with de-identified data (patient study number and date only).

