a. Primary outcome variable.

Pro-inflammatory cytokines: IL-1 β , TNF α , IL-6; Anti-inflammatory/repair factors: IL-10, BDNF

b. Secondary outcome variables will be measured at discharge and 30 days post-intracerebral hemorrhage or acute ischemic stroke.

- Modified Rankin Scale (mRS)
- Barthel Index will be measured at discharge and 30 days
- Medical Research Council Sum Score and dynamometry to measure muscle strength
- Discharge location (e.g., home, nursing facility), although not well studied, is commonly associated with physical function at discharge.
- SF-12
- Vital signs (e.g., heart, rate, blood pressure, respiratory rate)
- Delirium positive days
- Hospital acquired infections (e.g., catheter associated urinary tract infection and central line associated blood stream infection)
- CSF cytokines and repair factors
- Stroke Impact Survey

c. Statistical plan including sample size justification and interim data analysis.

Sample size was calculated for a fully powered trial and 9% of this sample size will be used for this pilot according to Cocks' methodology.¹⁰ An effect size of 0.28 was used, based on a published single group observational study in critically ill patients with a primary outcome of cytokine change.⁴⁷ Detection of an effect size of 0.28 with power of 80% and an α of 0.05 requires a sample size of 400 for a full trial and 9% represents a pilot sample size of 36 participants. Due to the enrollment of two stroke phenotypes, ischemic and hemorrhagic, we will analyze each cohort separately, therefore 40 participants per cohort are required. Accounting for attrition, up to 100 participants may be consented in order to enroll up to 40 participants per cohort. Each cohort will have 20 participants in each of two arms, intervention and control. It is estimated that at least 3-5 patients will be enrolled per month over 18 months.

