Descriptive statistics will be used to report sociodemographic variables. Baseline characteristics will be compared between the two groups. If they are found to be similar, post-intervention outcomes will be compared between the groups. If the baseline characteristics are found to be different, an adjusted analysis as described below will be conducted. Mean (SD) or median (IQR) will be used to describe continuous variables, and frequency (%) will be used for categorical variables. Mean differences in cytokines between the three time points (baseline, day 3 and day 7) will be calculated for each participant in the intervention and control groups. We will also plot data over time by group. Assumptions of normality will be checked and appropriate parametric or non-parametric tests will be used to detect absolute mean differences due to the small sample size, with an a priori significance level of 0.05, although the primary aim of this study is to estimate effect size. Data quality will be ensured by analyzing all samples in duplicate and procurement of samples will be performed by the same investigator. Statistical analysis will be performed using Stata 14.0 (College Station, Texas).

Primary aim (1): To determine whether a regimen of twice daily 20-minute sessions of CE plus usual care administered to patients with sICH and AIS (n=20) increases cytokines of the M2 phenotype and decreases cytokines of the M1 phenotype within 10 days of sICH when compared to a similar group of patients with sICH receiving usual care only (n=20).

The effect size, absolute difference between the two groups and the standard error of the difference will be estimated. The standardized difference will be estimated using Cohen's d. A two-sample t-test will be used to detect differences between post-test outcomes. If the baseline outcome is different, an analysis of covariance (ANCOVA) will be used to compare the outcomes between the two groups adjusting for the baseline difference as a covariate.

Hypothesis: Patients in the CE group will demonstrate an increase in cytokines of the M2 phenotype and a decrease in the M1 phenotype when compared to the group receiving usual care only.

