Administration of cycle ergometry will be performed by the Principal Investigator or trained registered nurses (RN) who currently perform this therapy in the NCCU and have been trained in current personal protective equipment standards in the setting of the novel Coronavirus pandemic. These clinicians are in possession of reusable face shields and masks as part of their routine work. All clinicians performing the intervention will have documented competency using a standardized competency checklist including physiologic monitoring considerations, positioning and alignment of the patient in the cycle ergometer and considerations for the management of lines and tubes to mitigate risk of dislodgement. The applicant will observe the application and performance of CE performed by unit RNs during 10% of sessions to assure correct procedure. All procedures for applying the CE to the patient will be explained to the patient or family member(s) in attendance. A physical therapist is part of our study team and will provide consultation as needed regarding cycle ergometry. Standard disinfection of the ergometer, inclusive of current guidelines for prevention of Coronavirus transmission, will be performed at the conclusion of each session by the study team.

A recent prospective safety and feasibility study of supine cycle ergometry in critically ill patients found only one adverse event in 541 sessions (181 patients), dislodgement of a radial arterial line. Another recent prospective study of 20 patients in an NCCU with intracranial pressure monitoring, 3 of which had a diagnosis of sICH, found no significant increases in intracranial pressure. Since, cycle ergometry is currently available in the NCCU, we performed an internal retrospective evaluation of 23 patients with an

intraventricular catheter (intracranial pressure monitor) over 32 sessions receiving supine lower extremity cycle ergometry. This evaluation revealed no peripheral oxygen desaturation, hemodynamic instability and no increases in intracranial pressure requiring an end to the session or further treatment.

Procurement of blood specimens will occur in tandem with standard of care blood draws (phlebotomy or arterial line) when possible and will be drawn by the applicant or the registered nurse caring for the patient. CSF specimens will be obtained using a protocol developed by the sponsor for a previous clinical trial requiring CSF sampling from an external ventricular drain.

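### The handling rule puts dry ice before the centrifuge for whole blood; followed as written, it would make the serum cytokine and BDNF primary outcome unreliable in both arms

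*Combined protocol and SAP*

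**What the plan says.** Section 3a lists the blood, saliva and CSF specimens and then gives a single instruction for all of them: "All samples will be placed on dry ice, centrifuged and stored in a -70 degree Celsius freezer within 1 hour of obtaining the sample".

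Item a) of the same section describes the blood specimen as "A 2 teaspoon sample of the patient's serum on the day of enrollment", with two further collections in the seven-day period. It then says how it is obtained: "Blood samples will be collected from an existing arterial or central line or via venipuncture". What enters handling is therefore whole blood, although the item calls it serum.

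The primary objective concerns cytokine trajectories in serum and CSF. Study Statistics, a, names IL-1β, TNFα and IL-6 on the pro-inflammatory side and "Anti-inflammatory/repair factors: IL-10, BDNF" on the other. Table 1 assigns all five to the blood draw.

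Two other places touch on specimen quality. Study Statistics, c: "Data quality will be ensured by analyzing all samples in duplicate and procurement of samples will be performed by the same investigator". Section 6b (Steps taken to minimize the risks): "Procurement of blood specimens will occur in tandem with standard of care blood draws (phlebotomy or arterial line) when possible". The first concerns the assay and who procures the sample. The second concerns when blood is drawn and by whom. Neither gives processing steps. Section 6b also mentions a separate protocol, but only for obtaining CSF.

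**The concern.** Serum is what remains after whole blood has clotted and the clot and cells have been spun off. That needs clotting at a temperature above freezing, then centrifugation, then freezing. The rule names dry ice first and includes no clotting step.

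If staff follow it as written, cells and platelets rupture before separation and their contents enter the fraction that is assayed. BDNF is the most exposed marker, because platelets carry it and release it. It is also one of the two factors the trial expects to rise with exercise.

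The pilot's stated main purpose is to estimate an effect size for a later trial. Unreliable serum values undermine that estimate, and a sample lysed by freezing cannot be restored. CSF is not a general fallback, because it is collected only from patients who already have an external ventricular drain.

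**Working it through.** There is no stated figure to reproduce; this is mainly a comparison of text, with a count and two short pieces of algebra.

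**1. Order of steps.**
- Written for all samples (section 3a): dry ice, centrifuge, -70 °C freezer, within 1 hour.
- Needed for serum (general laboratory knowledge, not in the documents): clot, centrifuge, aliquot, freeze.
- Dry ice is at about -78 °C (a physical fact, not in the documents), which is colder than the -70 °C storage freezer. Blood placed on it before the spin is being frozen, not merely cooled.

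**2. Does other text correct the order?** Section 3a items a) to c), Table 1, Study Statistics a and c, and section 6b contain no clotting step, no separation before freezing, no wet ice or refrigeration, and no hemolysis check. No blood-processing manual is cited.

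**3. Samples covered.** Study Statistics, c, gives up to 40 participants in each of two cohorts. Table 1 gives three blood draws (study days 1, 3 and 7).

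40 × 2 × 3 = 240 samples at most.

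This counts samples under the rule. It does not estimate how many would be spoiled.

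**4. Can the stated safeguards detect lysis?** Write a duplicate reading as y_ij = T_i + s_i + e_ij, where T_i is the true circulating level in sample i, s_i the error from handling, and e_ij the assay error in well j.
- Difference between duplicates: y_i1 − y_i2 = e_i1 − e_i2. The handling error s_i cancels, so close agreement says nothing about it.
- Mean of duplicates: T_i + s_i + (e_i1 + e_i2)/2. The handling error remains in full.

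The second safeguard, a single investigator procuring all samples, is not what section 6b describes: there, blood may be drawn by the applicant or by the nurse caring for the patient. More than one person may therefore depend on the written sequence.

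**5. Effect on the planned estimate.** Study Statistics, c, uses Cohen's d. If handling error adds variance σ_s² independently of arm to a between-patient variance σ², then

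d_observed = Δ / √(σ² + σ_s²), which is smaller than Δ / σ.

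The standard error of the mean difference grows by the factor √(1 + σ_s²/σ²). The documents give nothing from which σ_s² could be set, so no number is put on this.

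**6. If staff in fact spin before freezing.** Clotting, spinning and freezer storage share the 60 minutes. Clotting time must therefore be shorter than 60 minutes by the time the later steps take, and longer than zero, since unclotted blood yields no serum. Within that window the plan fixes no value, so clotting time may vary between samples, and BDNF is released from platelets during clotting. Standardizing it fits the limit: a 30-minute clot leaves 60 − 30 = 30 minutes for the spin, aliquoting and freezing.

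**The case against.** The best defense is that the sentence is a loose list. It names three actions under one time limit and has no word such as before or then. Ice may have been meant instead of dry ice, or dry ice for transport after the spin. A frozen tube would also produce no serum layer, so whoever handled the first one would notice. An IRB form is not a laboratory manual, and trained staff may already process blood correctly.

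Much of this stands. A slip is plausible, and failed separation would probably be seen at the bench before any assay was run. A reader might infer that all 240 samples will be unusable or that the trial's readings are invalid. The documents do not support that, because they do not show how samples are actually handled.

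A reader might also infer bias in the exercise comparison. The rule is the same in both randomized arms, and nothing in the plan suggests it would be applied differently. Nor is there support for saying that lysis would overwhelm the circulating levels, since the documents give no figure for any of the five markers. Saliva and CSF contain few cells and would be much less affected, so the point is specific to blood.

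What does not stand is the idea that the text can be left alone. It is the only blood-handling instruction in the document, its written order gives the wrong result for serum, and no other section corrects it. That staff would notice and improvise is not a control on a primary outcome.

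**Conclusion.** The point holds as a defect in a stated rule. Followed as written, the sequence would freeze and lyse whole blood before serum is separated and make all five serum markers of the primary outcome unreliable. Up to 240 samples fall under it, assuming 80 participants each give three draws. The harm is to validity and noise in both arms, with no evident between-arm bias and no size of distortion available from the documents.

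The conclusion rests on two facts from outside the documents, both general knowledge: the temperature of dry ice, and the rupture of blood cells on freezing. It is conditional on the sentence being followed literally. Even if it is a slip, the missing clotting time leaves an avoidable source of variation in BDNF. The rule should be corrected before further blood is collected.

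**What to change.** Give blood its own instruction in section 3a, for example: allow to clot at a non-freezing temperature for one fixed, stated time (such as 30 minutes); centrifuge; aliquot the serum; then dry ice or the -70 °C freezer, all within 1 hour of the draw; record visible hemolysis. The 30 minutes is only an example; the sponsor's laboratory may choose another validated time that fits the hour. Reword item a) so that it describes a blood draw from which serum is prepared. Separate wording for saliva and CSF is optional.

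The Background section says enrollment was put on hold on March 16, 2020, and the document is dated 7/10/2020, so some samples may already be stored. The sponsor should document how these were actually processed and carry a processing flag in the dataset, so that any early/late difference can be identified.

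No extra sample or equipment is needed. The costs are a little record-keeping and, if earlier practice differed from the corrected rule, a possible processing difference between early and later samples. If staff already clot and spin before freezing, the change largely writes down current practice and fixes the clotting time.

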Enrollment of subjects within the original study framework was put on hold beginning on March 16, 2020 due to the necessary hospital response to prevent further spread of COVID-19 and to maximize resources to treat hospitalized patients. Adding a second control group where all variables except for biologic and survey data will allow comparison of three different care conditions, intervention plus usual care, usual care only and usual care only during a pandemic. Usual care in terms of study visit timing, number, and length may be different than pre-pandemic care paradigms due to staff redeployment and restructuring are care areas to support care during a disaster.

3. Study Procedures

- a. Study design, including the sequence and timing of study procedures (distinguish research procedures from those that are part of routine care).

This pilot study uses a randomized parallel group design to determine the difference in the expression of pro- and anti-inflammatory cytokines in response to this specific exercise intervention plus usual care versus usual care only. Patients will be enrolled on day 3 of illness and data will be collected for seven consecutive days. We seek to enroll a convenience sample of up to 100 consecutive patients with supratentorial sICH and acute ischemic stroke admitted to the Johns Hopkins Hospital Neurosciences Critical Care Unit (NCCU). Patients will be screened within 24-48 hours of arrival for eligibility according to the inclusion and exclusion criteria listed below. Informed consent will be obtained from the patient or legally authorized representative (LAR). The consenting process will be performed remotely via videoconference when possible.

Patients will be randomly assigned to the intervention plus usual care or usual care only group using a standard randomization schema generated by STATA 14.0 (College Station, Texas). The AIS and sICH cohorts will have separate randomization schemas.

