After enrollment, the Patient-Reported Outcomes Measurement Information System (PROMIS) Global Measure of Health v1.2 questionnaire for (pre-morbid health) will be administered to the patient or their LAR depending on the patient's ability to complete the form. At the last follow-up visit the patient or LAR will complete the Stroke Impact Survey. Additionally, the Sunnybrook Neglect Assessment Procedure will be administered to the patient on day 1 of the study, on transfer from the ICU or discharge from the hospital and at 30 days after the hemorrhage.³¹ If the patient is assessed as not having neglect at the time of enrollment or is found not to have neglect as measured by the assessment procedure then they will not have to complete this measure at subsequent time points.

The intervention group will receive two CE sessions per day after randomization with a unit owned cycle (Reck Motomed Letto, Germany). Sessions will be held at least 2 hours apart to allow for patient rest and activities of patient care. The clinician will set the device to an automatic program where passive cycling will be initiated and the device will provide resistance if the patient attempts to actively cycle. Vital signs (e.g., heart rate, blood pressure, pulse oximetry, intracranial pressure) will be monitored continuously by a study team member present at the bedside during the CE session, if an

Figure 1: Supine cycle ergometer

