Usual care in the NCCU consists of evaluation and treatment by physical and occupational therapists assigned to the neurosciences service when an order for evaluation and treatment is entered by medical providers. Patients may be seen up to 5 times per week depending on their level of participation and intensity of therapy required, however many patients with sICH particularly those in coma are treated by therapists 2 times per week. Nursing staff in the NCCU provide passive range of motion and progressive a patient's mobility from supine to upright positioning, sitting at the side of bed, transferring to chair, lift assisted transfer to chair and ambulation as the patient's condition allows. All usual care activities will be recorded by the study team via extraction from the medical record. Usual care during the pandemic is similar to the care described above however, due to resource constraints it is possible that care focused on mobility and recovery was reprioritized in order to provide acute and intensive care for other patients.

Table 1. Study Activities Schedule for the intervention and prospective control group

	Admission day 1-2	Study day 1 = hospital day 3	Study day 2 = hospital day 4	Study day 3 = hospital day 5	Study day 4 = hospital day 6	Study day 5 = hospital day 7	Study day 6 = hospital day 8	Study day 7 = hospital day 9	Day of ICU transfer	30 days after hemorrhage (-10, +30 days)
Screening, Inclusion/Exclusion, Consent	X									
Intervention and monitoring										
Cycle ergometry 20 minute sessions (twice each study day)		XX								
Vital signs (BP, HR, RR, SpO ² , ICP)		X	X	X	X	X	X	X		
Pain scores		X	X	X	X	X	X	X		
Physiologic outcomes for the intervention and control groups										
Blood draw (IL1- β , IL-6, TNF- α , IL-10, CRP, BDNF)		X		X				X		
Saliva sample for cortisol		X		X				X		
CSF sampling, if a external ventricular		X		X				X		

drain is in place										
Outcome measures										
Medical Research Council Sum Score (strength testing) ²¹		X		X				X	X	X
Grip strength		X		X				X	X	X
Modified Rankin scale score	X								X	X
Barthel Index ¹²									X	X
Sunnybrook Neglect Assessment Procedure (SNAP) ³¹		X							X This battery will only be completed if the patient was found to have neglect on the initial assessment.	X This battery will only be completed if the patient was found to have neglect on the initial assessment.
Questionnaires										

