Promis Global Measure of Health v1.2 to patient or legally authorized representative (LAR)		X								
Stroke										X

Impact Survey to patient or LOR										
---------------------------------	--	--	--	--	--	--	--	--	--	--

b. Study duration and number of study visits required of research participants.

The study will enroll patients for approximately two years. Each patient will receive study interventions or procedures depending on group assignment for 7 days, assessment of motor function and physical/cognitive functioning on transfer from the NCCU or 1 day after the last study day if the patient completed study activities outside of the NCCU and 30 days (-10 days, +30 days) after occurrence of sICH. We will allow a 30 day time period in which to contact the patient if they are not able to be contacted on the 30th day for a total study period of 60 days. If a patient is seen in clinic prior to the 30 day period after the hemorrhage, follow-up assessments will be performed at that time. The stroke service currently collects a modified Rankin score for all ischemic and hemorrhagic stroke patients at 90 days via phone as a standard of care. We will record this value for all patients in this study. If a patient is not scheduled for an in-person visit after discharge, only the 90 day modified Rankin scale will be collected as an outcome measure.

c. Blinding, including justification for blinding or not blinding the trial, if applicable.

This pilot trial cannot be blinded because of the use of the supine cycle ergometer which is a large piece of equipment introduced into the patients' rooms in the intervention group twice per day during the initial study period, however outcome measures at NCCU transfer and 30 days will be obtained by a study team member blinded to the participant's group assignment.

d. Justification of why participants will not receive routine care or will have current therapy stopped.

Current therapy will not be stopped. Participants will receive the study intervention in addition to usual care.

e. Justification for inclusion of a placebo or non-treatment group.

In order to detect a signal of cytokine modulation with the intervention regimen of supine cycle ergometry, a control group not receiving the intensive intervention regimen is necessary for comparison.

f. Definition of treatment failure or participant removal criteria.

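### The early mRS and Barthel Index have no single assessment day, so a difference in NCCU stay between groups can appear as a difference in early disability

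*Combined protocol and SAP*

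**What the plan says.** The protocol describes the early assessment of disability in several places, and they differ:

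- Section 3b, study duration: "on transfer from the NCCU or 1 day after the last study day if the patient completed study activities outside of the NCCU".
- Table 1: the column is headed "Day of ICU transfer" and carries mRS, Barthel, SNAP, MRC sum score and grip strength. It gives no alternative for patients who leave before study day 7.
- Section 3c, blinding: NCCU transfer only.
- Secondary objective (i) and Aim 2: NCCU discharge.
- Study Statistics, item b: "Secondary outcome variables will be measured at discharge and 30 days post-intracerebral hemorrhage or acute ischemic stroke". It does not say discharge from where.
- Section 3a, for SNAP only: "on transfer from the ICU or discharge from the hospital and at 30 days after the hemorrhage". SNAP is repeated only in patients with neglect at the initial assessment.

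Aim 2 is analysed in the same way as the primary aim: a two-sample t-test, replaced by ANCOVA on the baseline value if baseline differs. Neither includes time from stroke to assessment. Table 1 shows no baseline Barthel, so that outcome has no baseline value to adjust for.

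**The concern.** The day of NCCU transfer is set after randomisation. It depends on how ill the patient is and might depend on cycling. If patients are improving over these weeks, the arm that leaves the NCCU sooner is measured sooner and scores worse, and the arm that leaves later scores better. Neither needs an effect on function. A real benefit accompanied by a shorter stay would be partly hidden.

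The differing texts add a second problem. Two coordinators could each follow the protocol and assess the same patient several days apart, one of them during the exercise period.

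The retrospective pandemic cohort is the most exposed. It has no study days, so section 3b's alternative cannot apply to it. The protocol itself expects pandemic care to differ through redeployment and restructured care areas. An early score timed by NCCU exit may then partly reflect bed flow.

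**Working it through.** **The plan's own figure.** The only power calculation concerns cytokines: "Detection of an effect size of 0.28 with power of 80% and an α of 0.05 requires a sample size of 400". Two-sided, n per arm = 2(1.960 + 0.842)² / 0.28² = 200.2, rounded up to 201, or 402 in total. This agrees with 400 (200 per arm gives power 0.7996). Then 0.09 × 400 = 36, as stated: "9% represents a pilot sample size of 36 participants". These figures are not in dispute. The 0.28 serves below only as a yardstick, with "Each cohort will have 20 participants in each of two arms, intervention and control", for which the standard error of a standardised difference is about √(2/20) = 0.32.

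**One patient under two texts.** The plan says "Patients will be enrolled on day 3 of illness and data will be collected for seven consecutive days", and Table 1 equates study day 1 with hospital day 3 and study day 7 with hospital day 9. The regimen is 7 × 2 = 14 sessions. For a patient who transfers on hospital day 5 (study day 3) and completes study activities on the ward:

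- Table 1: assessed on hospital day 5, after at most 3 × 2 = 6 sessions; 6/14 = 43%.
- Section 3b: assessed 1 day after hospital day 9, on hospital day 10, after the regimen.

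A patient who stays in the NCCU until hospital day 20 is assessed on day 20 under either text.

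**Size of the artefact.** Spurious difference (SD) = recovery rate (SD per day) × gap between arms in mean assessment day. The documents supply neither input, so both are assumed:

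- Transfer day is lognormal with log-SD 0.6 and median hospital day 7, 10 or 14, and never before day 3.
- Cycling shortens stay by 1, 2 or 3 days.
- Recovery is 0.02 to 0.10 SD per day.
- Cycling has no true effect on disability.

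Under Table 1 the assessment day is the transfer day. Under section 3b it is day 10 for anyone transferred by day 9 (all assumed to complete study activities), otherwise the transfer day. The lowest, middle and highest of the nine simulated combinations are:

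| Median transfer day | Stay shortened by (days) | Gap, Table 1 (days) | Gap, 3b (days) | Shift, Table 1 (SD) | Shift, 3b (SD) |
|---|---|---|---|---|---|
| 7 | 1 | 0.88 | 0.24 | 0.018–0.088 | 0.005–0.024 |
| 10 | 2 | 1.87 | 0.87 | 0.037–0.187 | 0.017–0.087 |
| 14 | 3 | 2.90 | 1.89 | 0.058–0.290 | 0.038–0.189 |

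For example, 0.10 × 1.87 = 0.187 and 0.10 × 0.87 = 0.087. At median day 10, the 10th to 90th percentile of assessment day is 4.6 to 21.6 under Table 1 and 10 to 21.6 under section 3b. Section 3b's rule removes the early tail and roughly halves the gap, but leaves the late tail. With one fixed day for everyone, the gap and the shift are zero by construction.

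**The case against.** The strongest reply is that section 3b is the detailed rule and the other texts are shorthand. On that reading, a patient who leaves early and completes study activities is assessed after the regimen. This stands in part. A reader might infer that the plan as a whole measures early leavers before the seven days are over. The section 3b sentence does not support that. Mid-regimen assessment follows only from the texts that omit its second half, or for a patient who leaves and does not complete study activities. But the protocol does not say which text governs, and the reply leaves patients who stay beyond study day 7 without a fixed day.

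The reply also rightly limits the scope. Table 1 measures MRC and grip on study day 7 as well, so strength has a comparison at a common time. The section 3a wording concerns SNAP alone. The Aim 2 disability hypothesis names the 90-day mRS, to be recorded for all patients. mRS and Barthel are scheduled again around 30 days, although section 3b collects only the 90-day mRS when no in-person visit is scheduled. For those patients the early Barthel is the only one.

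It is also fair to say that sicker patients being measured later does not by itself bias a randomised comparison, because severity is balanced in expectation. Bias between the randomised arms needs cycling to change NCCU stay, and the documents do not show that it does. Finally, every simulated shift is below the 0.32 standard error in a single cohort. That standard error reflects chance, however, while the shift is systematic, and the stated main purpose of this pilot is to estimate effect size.

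**Conclusion.** The point holds for early mRS and Barthel, and for SNAP in patients with neglect at the initial assessment. Their timing is stated inconsistently. Even on the most favourable text it is open-ended for patients who remain in the NCCU, and the analysis does not allow for it. A difference in NCCU stay can therefore pass for a difference in early disability.

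The size cannot be settled from the documents. Under the assumptions shown it is about 0.005 to 0.19 SD with section 3b's rule and 0.02 to 0.29 SD with Table 1's. Converting it to Barthel points would need a daily recovery rate that the protocol does not give. It would also need the gap in stay to carry over in full to the gap in assessment day, which section 3b's rule prevents.

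A reader might go further and conclude that the trial's disability result is compromised. The documents do not support that: the 90-day mRS is untouched, strength is less affected, and these are secondary outcomes of a pilot. The change is worth making because it is cheap.

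**What to change.** State one rule for the randomised arms and use it in secondary objectives (i) and (iv), sections 3a (SNAP), 3b and 3c, Table 1, Study Statistics item b and Aim 2. Extend section 3b's own alternative to everyone: early mRS, Barthel and SNAP on the day after study day 7 (hospital day 10 on the Table 1 clock), wherever the patient is, or at hospital discharge if earlier, with the date recorded. Use the study-day-7 MRC and grip as the end-of-regimen strength comparison. Report NCCU-transfer status and length of stay descriptively.

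For the retrospective cohort, which section 3a limits to what the chart records, take the charted score nearest that day, report its date, and treat the early three-group comparison as descriptive.

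The cost is wording. An existing blinded assessment moves, none is added, and the sample size is unchanged. The downsides are:

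- Early scores will cluster at the severe end of mRS and Barthel.
- The discharge exception leaves some variation in timing and still allows assessment before the regimen ends.
- The timepoint named in the objective, NCCU discharge, changes.
- Section 3a mentions the day-seven strength tests only for the control group and places them before that day's first session (at most 6 × 2 = 12 of 14 sessions). Section 3c promises blinding only at transfer and 30 days. Both need aligning with Table 1 and the new rule.
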